8.6 Experimental vaccine

The experimental **SARS-CoV-2 Vaccine (Vero cells), Inactivated** and the placebo were jointly developed by Shenzhen Kangtai Biological Products Co., Ltd. and Beijing Minhai Biotechnology Co., Ltd., and have passed the inspection of the National Institutes for Food and Drug Control.

8.6.1 Experimental vaccines

Medium-dose experimental vaccine: in a liquid dosage form, 0.5 ml/dose, containing 5 µg of SARS-CoV-2 protein.

High-dose experimental vaccine: in a liquid dosage form, 0.5 ml/dose, containing 10 µg of SARS-CoV-2 protein.

8.6.2 Placebo

In a liquid dosage form, 0.5 ml/dose, containing 0.25 mg of aluminum hydroxide adjuvant.

8.7 Clinical endpoints

8.7.1 Primary endpoints

- “the positive seroconversion rate and antibody level of neutralizing antibody against COVID-19 virus 28 days after the whole immunization”
- The positive seroconversion rate of IgG antibody (ELISA method) against COVID-19 virus 28 days after the whole immunization

8.7.2 Secondary endpoints

- Incidence of adverse events within 28 d after each dose of vaccine.

- Incidence of serious adverse events from the first dose to 12 months after full-course immunization.
- The antibody level of IgG antibody (ELISA method) against COVID-19 virus 28 days after the whole immunization
- Positive seroconversion rate and antibody level of neutralizing antibody and IgG antibody (ELISA method) against COVID-19 virus 28 days after the 2nd dose (as for 3-dose immunization group) or 14 days after the whole immunization (as for 2-dose immunization group)
- Positive seroconversion rates and the levels of novel coronavirus neutralizing antibodies and IgG antibodies (ELISA method) at 3, 6 and 12 months after full-course immunization.

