8.8 Study plan

8.8.1 Phase II clinical study plan

For each age group, the phase II trial is only permitted, when safety and tolerability have been preliminary confirmed in the phase I trial 7 days after the 1st dose of the high-dose group.

Volunteers will be screened from the resident healthy adults aged 18 years and above in accordance with the principles of voluntary registration, informed consent, and compliance with inclusion and exclusion criteria. When enrolled, every subject will be given a code number and get the correspondingly numbered vaccine shot. Subjects in the 18-59-year-old group will receive the experimental vaccine or placebo according to the 2-dose 0-14 d or 0-28 d immunization schedule, or 3-dose 0-28-56 d immunization schedule, respectively. Subjects in the ≥ 60 -year-old group will receive the experimental vaccine or placebo according to the 3-dose 0-28-56 d immunization schedule. After each dose, the subjects need to stay on site for 30 min to see if there's any immediate response. During the following 7-day systematic follow-up observation, the subjects should record their daily observation results on the Diary Card. After each dose, subjects will receive a telephone visit on day 3 and an intensive visit on day 7 by the researchers, to verify the safety of the vaccination. Subjects should carry out safety observations on their own from days 8-28 after each vaccination. After each dose, subjects will receive a telephone visit on day 14, and an intensive visit on day 28 by the investigator, to verify the safety of the vaccination.

About 5 ml of venous blood will be collected from subjects in the 2-dose immunization group before the 1st dose and 14 and 28 d after whole immunization, and from subjects in the 3-dose immunization group before the 1st and 3rd dose and 28 d after whole immunization, respectively, in order to determine the serum antibody levels. See Tables 2-7 for visit time, time window and visit content for different age groups.

Table 2. Visit content and schedule for 0-28-56 d immunization group

Visit No.	V0	V1	V2	V3	V4	V5	V6	V7	V8	V9	V10	V11	V12	V13
Content	Pre-immune 0-7 d	Day 0	3-5 d after V1	7-8 d after V1	14-21 d after V1	28-35 d after V1	3-5 d after V5	7-8 d after V5	14-21 d after V1 天	28-35 d after V5	3-5 d after V9	7-8 d after V9	14-21 d after V9	28-35 d after V9
1	Informed consent	X												
2	Collection of demographic information	X												
3	IgG, IgM screening	X												

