	RT-PCR assay	X												
	Urine pregnancy test (for women of childbearing age)	X				X				X				
	Height, weight, blood pressure		X											
	Pre-immune body temperature measurement		X			X				X				
4	Vaccination screening		X			X				X				
5	Assignment of study number		X											
6	Blood collection for antibody testing		X							X				X

Visit No.	V0	V1	V2	V3	V4	V5	V6	V7	V8	V9	V10	V11	V12	V13
Content	Pre-immune 0-7 d	Day 0	3-5 d after V1	7-8 d after V1	14-21 d after V1	28-35 d after V1	3-5 d after V5	7-8 d after V5	14-21 d after V1 天	28-35 d after V5	3-5 d after V9	7-8 d after V9	14-21 d after V9	28-35 d after V9
7	Vaccination	X				X				X				
8	30-min stay for observation, safety observation training	X				X				X				
9	Distribution of safety observation equipment	X				X				X				
10	Safety follow-up visit		X	X	X	X	X	X	X	X	X	X	X	X
11	Review of the Diary Card			X		X		X		X		X		X
12	Collection of the Diary Card					X				X				X
13	Subjects readily report AEs of Grade 3 and above and SAEs	X		X		X		X		X		X		X
14	Record the Original Record Book	X		X		X		X		X		X		X

Table 3. Sample collection schedule for subjects in the 0-28-56 d immunization group

Sample	Visit	V0	V1	V5	V9	V13
	Duration (d)	Pre-immune 0-7 d	Before 1 dose immunization	Before 2 dose immunization	Before 3 dose immunization	28-35 d after 3 dose immunization
Venous blood	Antibody test		5ml		5ml	5ml
Fingertip blood	IgG, IgM screening	Right amount				
Throat swab	RT-PCR assay	Right amount				
Urine sample (for women of childbearing age)	Urine pregnancy test	10ml		10ml	10ml	

Table 4. Visit content and schedule for 0-14 d immunization group

Visit No.	V0	V1	V2	V3	V4	V5	V6	V7	V8
Content	Pre-immune 0-7 d	Day 0	3-5 d after V1	7-8 d after V1	14-21 d after V1	3-5 d after V4	7-8 d after V4	14-21 d after V4	28-35 d after V4
1	Informed consent	X							
2	Collection of demographic information	X							
3	IgG, IgM screening	X							
	RT-PCR assay	X							
	Urine pregnancy test (for women of childbearing age)	X				X			
	Height, weight, blood pressure		X						
	Pre-immune body temperature measurement		X			X			
4	Vaccination screening		X			X			
5	Assignment of study number		X						
6	Blood collection for antibody testing		X					X	X
7	Vaccination		X			X			
8	30-min stay for observation, safety observation training		X			X			
9	Distribution of safety observation equipment		X			X			
10	Safety follow-up visit			X	X	X	X	X	X
11	Review of the Diary Card				X	X		X	X

Visit No.	V0	V1	V2	V3	V4	V5	V6	V7	V8

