10.4.2 Observation time and method of adverse reaction

Subjects should be observed for immediate response at the inoculation site for 30 min after each must dose of vaccine, local / systemic adverse events within this period shall be recorded. Emergency equipment, drug and healthcare professional shall be available on site. The investigator shall closely follow the subjects within 7 days after each vaccination, ask the subjects to carry out safety observations on their own, the observation results shall be recorded on the daily diary card by the subjects. Subjects will be visited intensively by the investigator at day 7 after each vaccination to verify safety observations. Subjects shall carry out safety observations on their own from days 8-28 after each vaccination, and record the observation results on the daily diary card. Subjects will be visited intensively by the investigator at day 28 after each vaccination to verify safety observations.

During the study period, the serious adverse events shall be observed by initiative report of the subjects and regular visits of the investigators. The researchers shall carry out investigation and verification, and handle well after receiving serious adverse events reports A visit (face to face/telephone visit) will be conducted once each at 3, 6, 9 and 12 months after immunization to collect the data on the incidence of SAEs.

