10.7.3 Analysis data set

10.7.3.1 Safety set

Safety set (SS): all subjects who have received at least one dose of the experimental vaccine are included. For those with wrong vaccination number, safety evaluation will be conducted according to the vaccine group actually administered by the subjects following the principle of ASaT (All Subjects as Treated). SS is mainly used for safety evaluation of vaccines.

This experiment will define the SS of each dose separately based on the safety analysis after different doses of vaccination.

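### In the 0-14 d cohort, the 28-day adverse-event window after dose 1 overlaps the dose-2 window by 7 to 14 days, so dose-1 incidence as written includes dose-2 reactions

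*Protocol*

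**What the plan says.** The secondary endpoint in Protocol 8.7.2 is "Incidence of adverse events within 28 d after each dose of vaccine", with no distinction by schedule. The protocol summary carries the same endpoint.

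Section 8.8.1 runs three schedules in adults aged 18-59, "according to the 2-dose 0-14 d or 0-28 d immunization schedule, or 3-dose 0-28-56 d immunization schedule, respectively". The group aged 60 and over "will receive the experimental vaccine or placebo according to the 3-dose 0-28-56 d immunization schedule".

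Observation is described in the same terms for all of them. Section 8.8.1 says "Subjects should carry out safety observations on their own from days 8-28 after each vaccination" and "After each dose, subjects will receive a telephone visit on day 14, and an intensive visit on day 28 by the investigator". Section 10.4.2 repeats that "Subjects will be visited intensively by the investigator at day 28 after each vaccination to verify safety observations".

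The visit plan for the short schedule is in "Table 4. Visit content and schedule for 0-14 d immunization group". There, dose 2 (V4) falls 14 to 21 days after dose 1 (V1), and every later visit (V5 to V8) is timed from V4. No visit is defined as 28 days after dose 1.

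On analysis, 10.7.3.1 says "This experiment will define the SS of each dose separately based on the safety analysis after different doses of vaccination". Section 10.7.4.4 reports events, cases and incidence per group, describes how adverse events are distributed over the doses, and compares groups by Fisher's exact test.

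**The concern.** A 28-day window after each dose separates the doses only if they are at least 28 days apart. In the 0-14 d cohort they are not. The last part of the dose-1 window is also the start of the dose-2 window, which includes the 30-minute on-site observation and the period of daily diary recording after dose 2.

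A table of dose-1 incidence built to the endpoint as written would therefore mix reactions to two doses in this cohort, while the same table for the other schedules would not. A reader who sets dose 1 beside dose 2 within the cohort, or dose 1 beside dose 1 across cohorts, would see a distortion caused by the window definition. An event soon after dose 2 meets the definition for both doses, and the protocol does not say which dose it belongs to.

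A smaller matter goes with it: the text promises an investigator visit on day 28 after each dose, and Table 4 has none defined for dose 1 of this cohort.

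**Working it through.** The protocol gives no figure for overlap or total observation time, so there is none of its own to reproduce.

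**Inputs.** Window length is 28 days after each dose (8.7.2). Dose 2 is 14 to 21 days after dose 1 in the 0-14 d cohort (Table 4). Successive doses are 28 to 35 days apart in the other schedules (Tables 2 and 6). The vaccination day counts as the first day of its window.

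**Overlap.** With dose 2 on day d, overlap = max(0, 28 - d) and, for d up to 28, calendar days covered = d + 28.

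| Schedule | Dose days | Sum of windows | Days covered | Overlap |
|---|---|---|---|---|
| 0-14 d, dose 2 earliest | 0, 14 | 56 | 42 | 14 |
| 0-14 d, dose 2 latest | 0, 21 | 56 | 49 | 7 |
| 0-28 d, nominal | 0, 28 | 56 | 56 | 0 |
| 0-28 d, latest | 0, 35 | 56 | 56 | 0 |
| 0-28-56 d, nominal | 0, 28, 56 | 84 | 84 | 0 |
| 0-28-56 d, latest | 0, 35, 70 | 84 | 84 | 0 |

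The overlap is 7/28 = 25% to 14/28 = 50% of the dose-1 window, and it occurs only in the 0-14 d cohort.

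**Effect on dose-1 incidence.** Let p be the probability of an event between dose 1 and dose 2, and q the probability of an onset in the overlap, taken as independent. The literal dose-1 incidence is 1 - (1 - p)(1 - q), which exceeds p by q(1 - p). The protocol gives no adverse-event rate, so the effect is sized here in days and not in percentage points.

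**Is day 28 after dose 1 observed?** V8 is 28 to 35 days after dose 2, so at the earliest on day 14 + 28 = 42. All 28 days after dose 1 are under follow-up.

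**Does a Table 4 visit fall near day 28 after dose 1?** With dose 2 on day 14, V7 (14 to 21 days after V4) falls on days 28 to 35. With dose 2 on day 21, V6 (7 to 8 days after V4) falls on days 28 to 29 and V7 on days 35 to 42. A contact can therefore fall there, but none is set for that purpose and all come after dose 2.

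**Only if any-dose incidence is shown across schedules.** Nominal days covered are 42, 56 and 84. Under an assumed constant background rate r per 28 days, incidence over t days is 1 - (1 - r)^(t/28):

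| Assumed r | 42 days | 56 days | 84 days |
|---|---|---|---|
| 5% | 7.4% | 9.8% | 14.3% |
| 10% | 14.6% | 19.0% | 27.1% |
| 20% | 28.4% | 36.0% | 48.8% |

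These differences come from observation time alone. They illustrate a comparison that the protocol does not specify.

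**The case against.** The strongest reply is that assigning events to doses is ordinary content of a statistical analysis plan, which 10.7.1 announces and which is not shown. That is fair as far as a missing rule goes. The point does not rest on the missing rule, however. The endpoint as worded in the protocol places an overlap event in both windows, and a later rule giving it to one dose would narrow the stated endpoint.

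Three stronger readings are tempting, and the documents do not support them.

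- *The dose-1 window cannot be measured.* Follow-up runs to at least day 42. What is lost is a window free of dose 2.
- *Events are double-counted.* No passage adds up the per-dose counts, and an any-dose incidence at subject level counts each subject once. Double counting is possible in per-dose tables for this one cohort, but it is not prescribed.
- *The schedules' incidences are not comparable, so the safety analysis is biased.* Each schedule randomises 2:2:1 to medium dose, high dose and placebo (8.3). Arms within a schedule therefore have the same planned time at risk and the same overlap. Section 10.7.4.4 does not say which groups it tests, and no cross-schedule test of adverse events is specified.

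It can also be said that the conflict over the day-28 visit is mostly one of wording, because V7 or V6 may fall close to day 28. That stands in part: the conflict is small, but the text allows no exception for this cohort and the table defines no such visit.

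**Conclusion.** The point holds for per-dose adverse-event incidence in the 0-14 d cohort. As written, 7 to 14 of the 28 days after dose 1 also belong to dose 2. Dose-1 incidence therefore takes in early dose-2 reactions, and an event in the overlap can appear under both doses. This rests on a literal reading of the endpoint together with the per-dose safety sets, and on dose 2 being given within the Table 4 window. An attribution rule in the unseen statistical analysis plan could settle the practice but would leave the protocol's wording ambiguous.

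Vaccine-placebo contrasts of any-dose incidence within a schedule are not affected. A dose-1 contrast within the 0-14 d cohort stays balanced in observation time, but it is not a contrast of dose 1 alone. A reader might infer from the 42, 56 and 84 days that the planned analysis favours the shorter schedule. It does not, because no such comparison is specified. The figures matter only if someone later sets any-dose incidences side by side.

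**What to change.** 1. In 8.7.2 or 10.7.4.4, state for per-dose incidence that each window runs from the dose to day 28 or to the next dose, whichever is earlier, and that each event is attributed to the most recent dose before onset. Carry the wording into the protocol summary. The cost is one or two sentences, with no change to doses or visits. The downside is that the dose-1 window in the 0-14 d cohort becomes 14 to 21 days, which should be stated wherever it is shown beside other schedules.

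2. Reconcile the day-28 visit text in 8.8.1, 10.4.2 and the protocol summary with Table 4 for the 0-14 d cohort. This is one sentence once the sponsor has settled what is intended.

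3. If any-dose incidence is ever shown across schedules, note that nominal observation is 42, 56 and 84 days (49 in the 0-14 d cohort when dose 2 is on day 21). Use days 0-7 after each dose, or events per person-time, for that display.

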8.8 Study plan

8.8.1 Phase II clinical study plan

For each age group, the phase II trial is only permitted, when safety and tolerability have been preliminary confirmed in the phase I trial 7 days after the 1st dose of the high-dose group.

Volunteers will be screened from the resident healthy adults aged 18 years and above in accordance with the principles of voluntary registration, informed consent, and compliance with inclusion and exclusion criteria. When enrolled, every subject will be given a code number and get the correspondingly numbered vaccine shot. Subjects in the 18-59-year-old group will receive the experimental vaccine or placebo according to the 2-dose 0-14 d or 0-28 d immunization schedule, or 3-dose 0-28-56 d immunization schedule, respectively. Subjects in the ≥ 60 -year-old group will receive the experimental vaccine or placebo according to the 3-dose 0-28-56 d immunization schedule. After each dose, the subjects need to stay on site for 30 min to see if there's any immediate response. During the following 7-day systematic follow-up observation, the subjects should record their daily observation results on the Diary Card. After each dose, subjects will receive a telephone visit on day 3 and an intensive visit on day 7 by the researchers, to verify the safety of the vaccination. Subjects should carry out safety observations on their own from days 8-28 after each vaccination. After each dose, subjects will receive a telephone visit on day 14, and an intensive visit on day 28 by the investigator, to verify the safety of the vaccination.

About 5 ml of venous blood will be collected from subjects in the 2-dose immunization group before the 1st dose and 14 and 28 d after whole immunization, and from subjects in the 3-dose immunization group before the 1st and 3rd dose and 28 d after whole immunization, respectively, in order to determine the serum antibody levels. See Tables 2-7 for visit time, time window and visit content for different age groups.

Table 2. Visit content and schedule for 0-28-56 d immunization group

Visit No.	V0	V1	V2	V3	V4	V5	V6	V7	V8	V9	V10	V11	V12	V13
Content	Pre-immune 0-7 d	Day 0	3-5 d after V1	7-8 d after V1	14-21 d after V1	28-35 d after V1	3-5 d after V5	7-8 d after V5	14-21 d after V1 天	28-35 d after V5	3-5 d after V9	7-8 d after V9	14-21 d after V9	28-35 d after V9
1	Informed consent	X												
2	Collection of demographic information	X												
3	IgG, IgM screening	X												
	RT-PCR assay	X												
	Urine pregnancy test (for women of childbearing age)	X				X				X				
	Height, weight, blood pressure		X											
	Pre-immune body temperature measurement		X			X				X				
4	Vaccination screening		X			X				X				
5	Assignment of study number		X											
6	Blood collection for antibody testing		X							X				X

Visit No.	V0	V1	V2	V3	V4	V5	V6	V7	V8	V9	V10	V11	V12	V13
Content	Pre-immune 0-7 d	Day 0	3-5 d after V1	7-8 d after V1	14-21 d after V1	28-35 d after V1	3-5 d after V5	7-8 d after V5	14-21 d after V1 天	28-35 d after V5	3-5 d after V9	7-8 d after V9	14-21 d after V9	28-35 d after V9
7	Vaccination	X				X				X				
8	30-min stay for observation, safety observation training	X				X				X				
9	Distribution of safety observation equipment	X				X				X				
10	Safety follow-up visit		X	X	X	X	X	X	X	X	X	X	X	X
11	Review of the Diary Card			X		X		X		X		X		X
12	Collection of the Diary Card					X				X				X
13	Subjects readily report AEs of Grade 3 and above and SAEs	X		X		X		X		X		X		X
14	Record the Original Record Book	X		X		X		X		X		X		X

Table 3. Sample collection schedule for subjects in the 0-28-56 d immunization group

Sample	Visit	V0	V1	V5	V9	V13
	Duration (d)	Pre-immune 0-7 d	Before 1 dose immunization	Before 2 dose immunization	Before 3 dose immunization	28-35 d after 3 dose immunization
Venous blood	Antibody test		5ml		5ml	5ml
Fingertip blood	IgG, IgM screening	Right amount				
Throat swab	RT-PCR assay	Right amount				
Urine sample (for women of childbearing age)	Urine pregnancy test	10ml		10ml	10ml	

Table 4. Visit content and schedule for 0-14 d immunization group

Visit No.	V0	V1	V2	V3	V4	V5	V6	V7	V8
Content	Pre-immune 0-7 d	Day 0	3-5 d after V1	7-8 d after V1	14-21 d after V1	3-5 d after V4	7-8 d after V4	14-21 d after V4	28-35 d after V4
1	Informed consent	X							
2	Collection of demographic information	X							
3	IgG, IgM screening	X							
	RT-PCR assay	X							
	Urine pregnancy test (for women of childbearing age)	X				X			
	Height, weight, blood pressure		X						
	Pre-immune body temperature measurement		X			X			
4	Vaccination screening		X			X			
5	Assignment of study number		X						
6	Blood collection for antibody testing		X					X	X
7	Vaccination		X			X			
8	30-min stay for observation, safety observation training		X			X			
9	Distribution of safety observation equipment		X			X			
10	Safety follow-up visit			X	X	X	X	X	X
11	Review of the Diary Card				X	X		X	X

Visit No.	V0	V1	V2	V3	V4	V5	V6	V7	V8
Content	Pre-immune 0-7 d	Day 0	3-5 d after V1	7-8 d after V1	14-21 d after V1	3-5 d after V4	7-8 d after V4	14-21 d after V4	28-35 d after V4
12	Collection of the Diary Card				X				X
13	Subjects readily report AEs and SAEs of grade 3 and above	X		X	X		X	X	X
14	Record the Original Record Book	X		X	X		X	X	X

Table 5. Sample collection schedule for subjects in the 0-14 d immunization group

Sample	Visit	V0	V1	V4	V7	V8
	Duration (d)	Pre-immune 0-7 d	Before 1 dose immunization	Before 2 dose immunization	After 2 dose immunization 14-21 d	After 2 dose immunization 28-35 d
Venous blood	Antibody test		5ml		5ml	5ml
Fingertip blood	IgG, IgM screening	Right amount				
Throat swab	RT-PCR assay	Right amount				
Urine sample (for women of childbearing age)	Urine pregnancy test	10ml		10ml		

Table 6. Visit content and schedule for 0-28 d immunization group

Visit No.	V0	V1	V2	V3	V4	V5	V6	V7	V8	V9
Content	Pre-immune 0-7 d	Day 0	V1 3-5 d	7-8 d after V1	14-21 d after V1	28-35 d after V1	3-5 d after V5	7-8 d after V5	14-21 d after V5	28-35 d after V1
1	Informed consent	X								
2	Collection of demographic information	X								
3	IgG, IgM screening	X								
	RT-PCR assay	X								
	Urine pregnancy test (for women of childbearing age)	X				X				
	Height, weight, blood pressure		X							
	Pre-immune body temperature measurement		X			X				
4	Vaccination screening		X			X				
5	Assignment of study number		X							
6	Blood collection for antibody testing		X						X	X
7	Vaccination		X			X				
8	30-min stay for observation, safety observation training		X			X				
9	Distribution of safety observation equipment		X			X				
10	Safety follow-up visit			X	X	X	X	X	X	X
11	Review of the Diary Card				X	X		X		X
12	Collection of the Diary Card					X				X
13	Subjects readily report AEs and SAEs of grade 3 and above		X		X	X		X	X	X
14	Record the Original Record Book		X		X	X		X	X	X

Table 7. Sample collection schedule for subjects in the 0-28 d immunization group

Sample	Visit	V0	V1	V5	V8	V9
	Duration (d)	Pre-immune 0-7 d	Before 1 dose immunization	Before 2 dose immunization	After 2 dose immunization 14-21 d	After 2 dose immunization 28-35 d
Venous blood	Antibody test		5ml		5ml	5ml
Fingertip blood	IgG, IgM screening	Right amount				
Throat swab	RT-PCR assay	Right amount				
Urine sample (for women of childbearing age)	Urine pregnancy test	10ml		10ml		

